### 7.2 Secondary Efficacy Analyses

Similar summaries and analyses will be carried out for the continuous secondary efficacy variables, assessing change from baseline and percent change from baseline in LDL-C (change from baseline only), non-HDL-C, TC, TG, HDL-C, VLDL-C, ApoB, ApoA-I, ApoA-II, ApoC-II, ApoC-III, ApoE, Lp(a), hsCRP, and fibrinogen at each scheduled time point. Sub-group analyses

will be performed for LDL-C, non-HDL-C, TC, TG, HDL-C, and VLDL-C, according to receptor mutation status. The FAS will also be used for the summary and analysis of the secondary efficacy endpoints.

Descriptive statistics, including the count and percentage, will be obtained for patients achieving LDL-C reduction of  $\geq 15\%$ ,  $\geq 20\%$ ,  $\geq 25\%$ , and  $\geq 30\%$  at each visit, with the focus being on Day 28, Day 56, and Day 84 using the FAS. Similar analyses will be obtained for patients achieving an LDL-C value  $< 100$  mg/dL (2.59 mmol/L) at Day 28, Day 56, Day 84, and at any time during the study.

### 7.3 Exploratory Efficacy Analyses

CI

## 8 ANALYSIS OF SAFETY

Safety will be assessed using the SP. The assessment of safety will include adverse events, clinical laboratory assessments, ECGs, physical examinations, and vital signs. The safety analysis will be based primarily on the frequency of new or worsening adverse events, laboratory abnormalities, and SAEs. Other safety data will be summarized as appropriate.

### 8.1 Extent of Exposure

Patients will be instructed to take study drug daily according to the protocol and return used and unused packaging to the site at each subsequent study visit.

Compliance with administration of study drug will be assessed by means of tablet counts based on the assessment of empty bottles returned to the site at each study visit after Day 1 during the Treatment Period and the ET Visit, if applicable.

Days of exposure to study drug will be summarized with descriptive statistics by treatment group for the Safety population.

Days of possible exposure, within a given dose level, is defined as the date of last dose of study drug minus the date of first dose of study drug plus 1. When the last known dose date is missing, the last known clinic visit date will be used.

Percent compliance with the study drug will be summarized by treatment group for the SP using descriptive statistics. Within a given dose level, compliance will be calculated by the total number of tablets taken divided by the total number of tablets presumed taken during the treatment period times 100. The total number of tablets taken is calculated by the total number of tablets dispensed minus the total number of tablets returned. The total number of tablets presumed taken is calculated by the number of days during the treatment period times the number of tables scheduled to be taken daily for the treatment period (i.e. 1 tablet for 300 mg period, 2 tables for the 600 mg period, and 3 tables for the 900 mg period).

The analysis will include listings for drug exposure and compliance.

## **8.2 Adverse Events**

AEs will be coded using the most recent version of the Medical Dictionary for Regulatory Activities (MedDRA) and summarized by treatment group, system organ class, and preferred term.

A summary overview of TEAEs will be provided which presents the number and percentage of patients in each treatment group satisfying each of the following categories:

- All TEAEs,
- Drug-related TEAEs,
- Maximum severity of TEAEs,
- Maximum severity of drug-related TEAEs,
- All treatment-emergent SAEs,
- Drug-related treatment-emergent SAEs,
- Death due to TEAEs,
- TEAEs leading to study drug discontinuation, and
- Drug-related TEAEs leading to study drug discontinuation.

The numbers and percentages of patients with TEAEs will be summarized by MedDRA preferred term within system organ class, by treatment group and overall. For the summaries by treatment group, multiple AEs with the same MedDRA preferred term within system organ class from the same patient within a given treatment will only be counted once. For overall summaries, multiple AEs with the same MedDRA preferred term within system organ class from the same patient will only be counted once. The AE onset date will determine the treatment group classification for the AE.

All TEAEs related to study drug, SAEs, and AEs leading to study drug discontinuation will be summarized in the same manner. Summaries will also be provided for the numbers and percentages of patients by system organ class, preferred term, and maximum severity, for TEAEs and drug-related TEAEs.

All AEs will be included in by-patient listings containing additional information of interest such as onset and resolution times, maximum severity, causal relationship to study medication, and action taken. Specific by-patient listings of SAEs and TEAEs leading to study discontinuation will be provided.

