5 STUDY TREATMENTS

5.1 Treatment Groups

During the 12-week Treatment Period, all patients will receive gemcabene 300 mg QD for 4 weeks, followed by 600 mg QD for 4 weeks, followed by 900 mg QD for 4 weeks.

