Any medical condition already present prior to the patient taking the first dose of study drug (Day 1) should be reported in the medical history. Any SAEs occurring prior to the first dose of study drug (Day 1) should be reported as an update to medical history as well as an adverse event. Any pre-existing medical condition or signs or symptoms that changes in severity, frequency, or seriousness after the patient takes the first dose of study drug (Day 1) and through the Follow-up Visit should be reported as an adverse event.

Clinically significant abnormal laboratory values or other examinations (e.g., ECG) that are detected at the time of the first dose of study drug (Day 1) and worsen during the study should be reported as adverse events. An abnormal laboratory result that is not verified by repeat testing does not necessitate reporting as an adverse event. The Investigator will exercise his or her medical, scientific, and clinical judgment in deciding whether an abnormal laboratory finding or other abnormal assessment is clinically significant. Clinically significant abnormal laboratory values occurring during the clinical study will be followed until repeat tests return to normal, stabilize, or are no longer clinically significant. Any abnormal test that is determined to be an error does not require reporting as an adverse event.

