### 2.2 Trial Design

This is a Phase 2, open-label, dose-finding, 3-period, 3-treatment study using successively escalating doses of 300 mg, 600 mg, and 900 mg gemcabene in patients with HoFH. All patients will be on each of the successive doses for 4 weeks at a time. Patients will remain on their current

stable, lipid-lowering therapy throughout the study. Patients will not be allowed in the study if they are undergoing apheresis or taking mipomersen or lomitapide.

The population for this study is male and female patients,  $\geq 17$  years of age, diagnosed with HoFH by genetic confirmation or a clinical diagnosis based on either (1) a history of an untreated LDL-C concentration  $>500$  mg/dL (12.92 mmol/L) together with either appearance of xanthoma before 10 years of age, or evidence of heterozygous familial hypercholesterolemia in both parents or, if history is unavailable, (2) LDL-C  $>300$  mg/dL (7.76 mmol/L) on maximally tolerated lipid-lowering drug therapy. Approximately 8 patients will be enrolled into the study. Total study duration will be up to 18 weeks and will consist of a Screening Visit, a Treatment Period, and a Follow-up Visit.

The Treatment Period is a sequential design whereby each patient will receive gemcabene 300 mg QD for 4 weeks. The same patients will then receive a 600 mg dose QD for 4 weeks and finally 900 mg dose QD for 4 weeks. There will be no interruptions in gemcabene dosing when changing from the 300 mg to the 600 mg dose or when changing from the 600 mg to the 900 mg dose unless there are clinically significant safety issues resulting in the temporary or permanent discontinuation of study drug. The first 300 mg dose of study drug will be administered at the site on Day 1. Assessments will be performed after the patient has been on the study drug for 2 weeks for each dosing level and on the last day of each dose.

The Follow-up Visit will occur 4 weeks ( $\pm 3$  days) after the last dose of study drug.

The schedule of events for the trial is provided in Table 1.

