### ***3.2.1 Adverse Events***

AEs will be assessed at all study visits and the Follow-up Visit. Adverse events that occur on or after the first dose of study drug (Day 1) will be considered treatment-emergent adverse events (TEAEs). Further details regarding AEs, such as the definition of an AE or serious adverse event (SAE), TEAEs, assessment of severity, assessment of causality, etc., are described in Section 9.1 and 9.2 of the protocol.

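### SAP 8.2 counts every adverse event under the dose at onset, so an event that stops treatment or turns serious after a dose step is tabulated under the lower dose

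*SAP*

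**What the plan says.** Protocol 5.1 fixes the sequence: "all patients will receive gemcabene 300 mg QD for 4 weeks, followed by 600 mg QD for 4 weeks, followed by 900 mg QD for" a last 4 weeks. SAP 2.2 adds that "There will be no interruptions in gemcabene dosing when changing from the 300 mg to the 600 mg dose", and the same sentence covers the step from 600 to 900 mg. Its only exception is a stop, temporary or permanent, for a clinically significant safety issue.

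SAP 8.2 then assigns events to dose columns: "The AE onset date will determine the treatment group classification for the AE". It continues: "All TEAEs related to study drug, SAEs, and AEs leading to study drug discontinuation will be summarized in the same manner". The overview table in that section also counts patients by treatment group for maximum severity, deaths and discontinuations, and no other date rule is given for it. SAP 3.2.1 defines treatment emergence against Day 1 only, not against the start of each dose.

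The by-patient listings are to carry "additional information of interest such as onset and resolution times, maximum severity, causal relationship to study medication, and action taken". No date of maximum severity is named.

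Two other statements touch on worsening. SAP 8 says: "The safety analysis will be based primarily on the frequency of new or worsening adverse events, laboratory abnormalities, and SAEs"; Protocol 10.2.3 says the same. Protocol 9.1 requires an adverse event report for "Any pre-existing medical condition or signs or symptoms that changes in severity, frequency, or seriousness after the patient takes the first dose" of study drug, in a paragraph about conditions present before dosing.

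**The concern.** Dating an event by its onset is a sound way to count new events. It is less suited to outcomes that come later in the life of an event. In parallel groups the distinction would hardly matter, because a patient stays in one column. Here each patient passes through all three columns, and an event can start in one and reach its outcome in another.

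Take a hypothetical case. Mild myalgia begins on Day 20 (300 mg period), and treatment is stopped for it on Day 70 (900 mg period). Kept as one record, it appears as a discontinuation under 300 mg, and 900 mg shows none.

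The by-dose tables matter because safety and tolerability are part of the primary objective, and the first secondary objective uses safety data to confirm the Phase 3 dose. Events that span dose steps are plausible on the protocol's own account. Protocol 1.3 lists myalgia and abnormal kidney function tests among the common events, and says creatinine rises appeared within the first 2 to 4 weeks, which in this design is the 300 mg period.

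**Working it through.** The plan states no figure on this point, so there is none to reproduce. The check is a reading of the rules followed by simple arithmetic.

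**1. Which date decides the column?** From SAP 8.2:
- New treatment-emergent events: onset date.
- Related events, SAEs and events leading to discontinuation: onset date, by the sentence that carries the same manner of summary over to them.
- Maximum severity in the overview by treatment group: no separate rule, so onset date is the only classifier available.
- Maximum severity by system organ class and preferred term: the sentence does not mention treatment group, so it is left out here.

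**2. Which way can the shift go?** An outcome cannot precede the onset of its event, and planned dose never falls. So dose at onset ≤ dose at outcome. Any difference moves the outcome from a higher dose column to a lower one, never the reverse.

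**3. How much does one patient move?** Assume the denominator is the number of patients treated on that dose. The planned number is about 8 (SAP 2.2). The lower case of 6 is the minimum number of completers that Protocol 4.3 seeks if more than 2 patients withdraw.
- 1/8 = 12.5 percentage points.
- 1/6 = 16.7 percentage points.

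For one discontinuation on 900 mg of an event that began on 300 mg, with 8 patients on each dose:
- By onset: 300 mg 1/8 (12.5%), 900 mg 0/8 (0%). Difference, 300 minus 900: +12.5 points.
- By dose when drug was stopped: 300 mg 0/8, 900 mg 1/8. Difference: −12.5 points.
- Change in the contrast: 12.5 − (−12.5) = 25 points.

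**4. A two-patient illustration (assumed, 8 per dose).** Both events start mild on 300 mg. Patient A's becomes severe and stops treatment on 900 mg. Patient B's becomes severe and serious on 600 mg.

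| Outcome | Rule | 300 mg | 600 mg | 900 mg |
|---|---|---|---|---|
| Severe | onset | 2 | 0 | 0 |
| Severe | dose at outcome | 0 | 1 | 1 |
| SAE | onset | 1 | 0 | 0 |
| SAE | dose at outcome | 0 | 1 | 0 |
| Discontinuation | onset | 1 | 0 | 0 |
| Discontinuation | dose at outcome | 0 | 0 | 1 |

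Under either rule the two mild onsets can still be counted at 300 mg.

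**5. Precision.** Exact (Clopper-Pearson) 95% intervals are 0.0 to 36.9% for 0/8 and 0.3 to 52.7% for 1/8. For 0/6 and 1/6 they are 0.0 to 45.9% and 0.4 to 64.1%.

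**6. Does anything else correct the by-dose tables?** No section of either document moves an event to a later dose, or clearly requires a new record when an event that began on study worsens after a dose step.

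**The case against.** Several points on the other side have weight.

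- **The recording convention is not visible.** The eCRF instructions are not in the documents, and SAP 5.4 places derived-data specifications elsewhere. If sites open a new record when an event worsens, most of the severity and SAE problem disappears. Protocol 9.1 could even be read so that a changed on-study symptom is reportable. This stands as a limit on the point. It does not settle discontinuation: an unchanged event that finally stops treatment on 900 mg keeps its 300 mg onset under any such convention.
- **Other outputs limit the harm.** There are by-patient listings, with separate ones for SAEs and for events leading to study discontinuation. Laboratory results are summarised by visit, so creatinine and CK values do not depend on event onset. With about 8 patients each case can be read individually. All true, but the by-dose tables stay as they are.
- **The size is 1/n applied to an assumed case.** The documents give no rate of events that span doses. Protocol 1.3 describes mostly mild to moderate events and no treatment-related SAEs. The intervals above overlap widely, and no formal by-dose comparison of events is planned. This stands.

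A reader might go further in three ways that the documents do not support. First, that SAP 8.2 contradicts SAP 8: the reference there to new or worsening events is general, and where the protocol explains worsening it does so mainly against the state before dosing. SAP 8.2 lacks a way to count worsening by dose, which is a gap and not a clear contradiction. Second, that the sentence extending the onset rule covers severity: it names related events, SAEs and discontinuations only, and severity is affected through the overview table. Third, that the tables would show 900 mg as best tolerated when the reverse was true: dose is confounded with time and cumulative exposure here, so neither rule establishes cause.

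**Conclusion.** The point holds for the by-dose tables. With complete and correct dates, SAP 8.2 places discontinuations and SAEs under the dose at onset, as it does maximum severity in the overview table. Any displacement in this design favours the higher dose. The size is 12.5 points per patient at 8 on the dose and 16.7 at 6.

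This rests on three assumptions: the event is kept as one record (needed for severity and seriousness, less so for discontinuation), it spans a dose step, and the denominator is the number treated on that dose. How often the second condition would be met is unknown. Overall columns are unaffected. Counting an outcome at the dose being taken when it occurred describes when it happened; it does not show that the dose caused it.

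**What to change.** In SAP 8.2:

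1. Keep onset date for the incidence of new treatment-emergent events.
2. Also tabulate events leading to study drug discontinuation by the dose being taken when drug was stopped. The inputs are already held: action taken (SAP 8.2 listings) and the last-dose date within each dose level (SAP 8.1).
3. Where the date an event worsened or became serious can already be found in AE or SAE records, also show severity and SAEs by the dose at that date. Where it cannot, flag in the listings any event that spans a dose step.

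Item 2 costs a sentence and one table. Item 3 is deliberately limited to existing dates. SAP version 1.0 is dated 7 June 2017, and by the first interim cut-off of 12 January 2017 two patients already had data through Week 12 and a third through Week 8 (SAP 10). Requiring a new severity-change date or a new record for everyone would therefore mean going back to source for completed patients.

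The downside is that an event can appear under two dose columns, which a footnote should say. The overall column still counts it once.

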## **8.3 Safety Laboratory Parameters**

Clinical chemistry, coagulation, hematology, and urinalysis results will be summarized with descriptive statistics at all visits with the focus on Day 28, Day 56, and Day 84. Change from baseline will also be summarized. Frequency counts of new or worsening abnormalities will also be provided. Laboratory values will also be listed by visit, within patient.

#### **8.4 Vital Signs**

Vital signs and the change from baseline will be summarized descriptively by visit. Vital sign data will also be listed by visit, within patient.

#### **8.5 ECG Parameters**

Electrocardiogram results will be summarized with counts and percentages by visit and results will also be listed.

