12. Uncontrolled cardiac arrhythmia or prolonged QT on the Screening Visit or Day 1 prior to dosing ECG (QTcF >450 msec for men and >470 msec for women) or known family history of prolonged QT or unexplained sudden cardiac death;
13. Uncontrolled hypertension, defined as sitting systolic blood pressure >180 mmHg or diastolic blood pressure >110 mmHg, and confirmed by repeat measurement;
14. Currently receiving cancer treatments or, in the Investigator's opinion, at risk of relapse for recent cancer;
15. Use of fibrate lipid-lowering agent 6 weeks prior to the Screening Visit;
16. Hypersensitivity to or a history of significant adverse reactions to any fibrate lipid-lowering agent;
17. Use of apheresis (LDL or plasma) 8 weeks prior to the Screening Visit;
18. Use of lomitapide 2 months prior to the Screening Visit;
19. Use of mipomersen 5 months prior to the Screening Visit;
20. Use of any excluded medications or supplements (e.g., potent cytochrome P450 [CYP] 3A4 inhibitors, see [Appendix D](#));

21. History of drug or alcohol abuse within the past year or inability to comply with protocol requirements, including subject restrictions (see [Section 5.6.3](#));
22. Previously treated with gemcabene;
23. Participation in another clinical study of an investigational agent or device concurrently or within 1 month prior to the Screening Visit, or use of an investigational agent within 1 month or 5 half-lives (if known), whichever is longer, prior to the Screening Visit; or
24. Any other finding which, in the opinion of the Investigator, would compromise the patient's safety or participation in the study.

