9.8 Electrocardiograms

Electrocardiograms will be performed in triplicate and sent to a central reviewer. Patients should be lying quietly in a fully supine position for at least 10 minutes prior to each 12-lead ECG. A 12-lead ECG will be performed at the Screening Visit and pre-dose on Day 1, Day 14, Day 42, Day 70, and the ET Visit, if applicable. Electrocardiograms will be performed pre-dose and 2 hours post-dose on Day 28, Day 56, and Day 84.

The Investigator will assess ECG data as normal, abnormal not clinically significant, or abnormal clinically significant. Any clinically significant abnormalities should be documented as medical history/adverse event/SAE as applicable. All ECG tracings will be kept as source data.

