### ***3.2.4 Electrocardiograms***

ECGs will be performed in triplicate and sent to a central reviewer. A 12-lead ECG will be performed at the Screening Visit and pre-dose on Day 1, Day 14, Day 42, Day 70, and the ET Visit, if applicable. Electrocardiograms will be performed pre-dose and 2 hours post-dose on Day 28, Day 56, and Day 84.

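### SAP 8.5 plans ECG counts and a listing, but no summary of QTcF or other intervals, no change from baseline, and no split of pre-dose from 2-hour ECGs

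*SAP*

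**What the plan says.** The whole planned ECG analysis is one sentence in SAP 8.5: "Electrocardiogram results will be summarized with counts and percentages by visit". The rest of that sentence provides for a listing.

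The data behind it are richer than that sentence suggests. SAP 3.2.4 states "ECGs will be performed in triplicate and sent to a central reviewer" and "Electrocardiograms will be performed pre-dose and 2 hours post-dose on Day 28, Day 56, and Day 84". Those three days are the last days on 300, 600 and 900 mg. Protocol 9.8 gives the remaining schedule: "A 12-lead ECG will be performed at the Screening Visit and pre-dose on Day 1, Day 14, Day 42, Day 70, and the ET Visit".

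The only ECG outcome that either document defines is categorical. Protocol 9.8 says "The Investigator will assess ECG data as normal, abnormal not clinically significant, or abnormal clinically significant". QTcF is named once, in exclusion criterion 12 of Protocol 4.2, as an entry limit on the Screening or Day 1 pre-dose ECG: "QTcF >450 msec for men and >470 msec for women".

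The neighbouring SAP sections go further. For vital signs, SAP 8.4 says "Vital signs and the change from baseline will be summarized descriptively by visit". SAP 8.3 plans descriptive statistics and change from baseline for laboratory results, and SAP 8.6 plans change from baseline for physical examinations.

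**The concern.** ECG is the only assessment in SAP 8.3 to 8.6 without a change-from-baseline summary, and neither document gives a reason. Yet the ECG schedule is built for one: replicate tracings, a central reviewer, a pre-treatment tracing on Day 1, and paired tracings around a dose at each of three dose levels. The 2-hour ECG also falls at the same nominal time as a scheduled PK sample on Days 28, 56 and 84 (Protocol 6.3.3, 6.3.5 and 6.3.7).

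Safety and tolerability are part of the primary objective (SAP 2.1.1), and safety data feed the choice of Phase 3 dose (SAP 2.1.2). A moderate shift in QTcF can occur without moving any patient from a normal to an abnormal category. With about 8 patients, a table of categories is therefore unlikely to show such a shift, and readers would have to reconstruct it from the listing.

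**Working it through.** The documents give no figure for ECG precision and no SD for QTcF, so there is no stated result to reproduce. The sample size of 8 rests on a general statement about precision for LDL-C (SAP 11).

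**1. What is planned, side by side**

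| SAP section | Summary planned | Change from baseline |
|---|---|---|
| 8.3 Laboratory | Descriptive statistics, frequency of abnormalities, listing | Yes |
| 8.4 Vital signs | Descriptive, listing | Yes |
| 8.5 ECG | Counts and percentages, listing | Not planned |
| 8.6 Physical examination | Summary by visit, listing | Yes |

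**2. What is collected** (Protocol 9.8, SAP 3.2.4)

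- Single time points: Screening and Days 1, 14, 42 and 70 = 5.
- Paired time points: Days 28, 56 and 84, two each = 6.
- Total: 5 + 6 = 11 time points per completer. In triplicate, 11 × 3 = 33 tracings per patient and 33 × 8 = 264 for 8 patients. Averaging triplicates gives 11 × 8 = 88 values.
- On each of Days 28, 56 and 84 a patient contributes 2 × 3 = 6 tracings to one visit.

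**3. What counts can show at this size**

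- One patient is 1/8 = 12.5%.
- With 0 of 8 abnormal, the exact two-sided 95% upper limit is 1 − 0.025^(1/8) = 0.369, or 36.9%.
- If the true rate were 10%, the chance of seeing 0 of 8 is 0.9^8 = 0.43.

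**4. What a mean change could show**

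Half-width of the 95% interval = t(0.975, n−1) × SD / √n. The SD of the QTcF change is an assumption, shown over a range. n = 8 is the planned enrolment. n = 6 is the number of completers that the replacement rule in Protocol 4.3 aims to secure.

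| Assumed SD (ms) | n = 8: 2.365 × SD / 2.828 | n = 6: 2.571 × SD / 2.449 |
|---|---|---|
| 8 | ±6.7 ms | ±8.4 ms |
| 10 | ±8.4 ms | ±10.5 ms |
| 15 | ±12.5 ms | ±15.7 ms |

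**5. What the sentence leaves open for the counts themselves**

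SAP 8.5 does not say which of the two time points on Days 28, 56 and 84 is counted, or how three tracings become one result. No ECG baseline is defined: the baseline rules in SAP 7 cover efficacy variables, and ECGs are taken at both Screening and Day 1. The rule for windows and unscheduled values in SAP 5.2 covers laboratory variables only.

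**The case against.** The strongest reply is that SAP 8.5 fits the one ECG variable the documents define. Counts and percentages are the natural summary of a three-category investigator assessment, and with about 8 patients the listing puts individual results in front of the reader. SAP 5.4 defers table shells and derivations to separate specifications, where triplicate averaging and time-point rows often sit, and SAP 8 allows other safety data to be summarised as appropriate. Protocol 1.3 reports no clinically relevant QTc effect so far, QTc is not an objective, and dose selection also draws on other studies (Protocol 3.1). The proposed mean would come from 6 to 8 patients with no control arm and a fixed 300, 600, 900 mg sequence, so a shift could not be attributed to dose.

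Much of this stands, and it rules out several stronger readings that a reader might infer:

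- That ECGs are reported only as counts, or that data are discarded. The same sentence promises a listing.
- That QTcF values are known to be centrally measured at every visit. The documents say that tracings go to a central reviewer but not which values come back.
- That pre-dose and 2-hour results are pooled. SAP 8.5 is silent on time point.

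It does not remove the gap. A listing is not a summary. Neither the general clause in SAP 8 nor the deferred specifications commit to an interval summary, whereas the adjacent sections commit to change from baseline in the SAP itself. Criterion 12 also requires QTcF before dosing, so it is obtained at least then.

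**Conclusion.** The point holds as a minor weakness in the analysis plan. For ECGs, SAP 8.5 states a method that is less informative than the one it uses for laboratory values and vital signs, although the schedule supports a better one. Category counts leave an upper limit of 36.9% when no patient is abnormal, whereas a mean QTcF change could be estimated to within about 7 to 12.5 ms at n = 8, or about 8 to 16 ms at n = 6.

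Those widths rest on an assumed SD of change of 8 to 15 ms, and the gain rests on the central reviewer returning interval values on treatment, which the documents do not describe. The summary would be descriptive: it could not separate dose from time or from other uncontrolled influences. The documents give no ground for inferring a QTc safety signal or a loss of ECG data.

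**What to change.** Amend SAP 8.5, for the interval values that the central reviewer returns:

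- Average the triplicates at each time point.
- Define the ECG baseline as Day 1 pre-dose.
- Summarise QTcF and its change from baseline descriptively by dose, visit and time point, with pre-dose and 2-hour post-dose shown separately on Days 28, 56 and 84.
- Add the within-visit change from pre-dose to 2 hours on those three days.
- Add counts above the protocol's 450/470 msec entry limits, labelled as descriptive reference values only, since the documents do not set them as on-treatment limits.
- Keep the existing counts and listing, and state which time point the counts use.

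The cost is one or two extra tables, with no new procedures or visits. The text should say that the results are descriptive, because there is no control arm and dose is confounded with time.
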